5.4.1 Rescreening

Results of screening assessments that do not meet the parameters required by eligibility criteria (e.g., clinical laboratory tests, vital signs, physical examination, electrocardiogram [ECG], etc) may be repeated once within the 28-day screening period without the need to register the participant as a screen failure. If the participant meets exclusion criteria that cannot resolve during the screening period, or more than 28 days elapse from the date of signing the ICF, the participant must be documented as a screen failure. In order to re-screen after prior screen failure, a new ICF must be signed and the participant will enter into screening with a new participant identification number. Rescreening is only allowed once for an individual participant after discussion with medical monitor. The Screening/baseline and safety assessments do not need to be repeated if they still within the acceptable procedure completed time frame and all results meet inclusion and no exclusion criteria.

6 INVESTIGATIONAL PRODUCT(S)

6.1 Investigational Product(s) Administered

Table 6 Investigational Product(s)

Name	Enfortumab vedotin
Use	test product
Dosage Form	lyophilized powder for reconstitution
Physical Description	white to off-white

Unit Dose Strength	30 mg of enfortumab vedotin in a single-dose vial
Packaging and Labeling	clear single use vial
Route of Administration	intravenous infusion
Administration	Administered intravenously over 30 minutes. Refer to Section 6.1.1 for additional details.
IMP or Non-IMP	IMP
Sourcing	provided centrally by sponsor

IMP: Investigational Medicinal Product.

The investigational product, enfortumab vedotin (ASG-22CE), is a sterile, preservative-free, white to off-white lyophilized powder to be reconstituted for IV administration. The investigational product is supplied by Astellas in single-use glass vials containing 30 mg enfortumab vedotin in each vial. The investigational product should be stored at 2°C to 8°C.

Refer to the pharmacy manual, product label and package insert for detailed information regarding preparation, handling and storage of the enfortumab vedotin.

6.1.1 Investigational Product Administration

Enfortumab vedotin at a dose of 1.25 mg/kg will be administered monotherapy as an IV infusion over approximately 30 minutes on Days 1, 8, and 15 of every 28-day cycle. In the absence of infusion related reactions (IRRs), the infusion rate for all participants should be calculated in order to achieve an approximate 30-minute infusion period.

Enfortumab vedotin must not be administered as an IV push or bolus. Enfortumab vedotin should not be mixed with other medications. At least 7 days must elapse between doses of enfortumab vedotin.

Participant weight must be measured during all relevant assessment time points as described in the [[Table 1](#) Schedule of Assessments]. Weight-based dosing is calculated using the participant's actual body weight on Day 1 of each cycle. The dose does not need to be re-calculated based on actual weight on Day 8 and 15 of each cycle unless it is required by institutional standards. **An exception to weight-based dosing is made for participants weighing greater than 100.0 kg; doses will be based on 100 kg for these individuals. The maximum dose permitted on this study is 125.0 mg.**

Participants should be observed during enfortumab vedotin administration and for at least 60 minutes following the infusion for the first 3 cycles. All supportive measures consistent with optimal participant care should be given throughout the study according to institutional standards.

The injection site should be monitored closely for redness, swelling, pain, and infection during and at any time after administration. Participants should be advised to report redness or discomfort promptly at the time of administration or after infusion. Events of extravasation should be managed per institutional guidelines and precautions should be taken to prevent extravasation per institutional standards.

6.2 Preparation/Handling/Storage/Accountability

6.2.1 Packaging and Labeling

All study drug(s) used in this study will be prepared, packaged and labeled under the responsibility of qualified personnel at sponsor's designee in accordance with sponsor's designee standard operating procedures (SOPs), current Good Manufacturing Practice (GMP) guidelines, International Council for Harmonisation of Technical Requirements for Pharmaceuticals for Human Use (ICH) Good Clinical Practice (GCP) guidelines and applicable local laws/regulations.

Each vial will bear a label conforming to regulatory guidelines, GMP and local laws and regulations that identifies the contents as investigational drug.

Refer to the pharmacy manual for detailed information regarding packaging and labeling of the enfortumab vedotin.

6.2.2 Handling, Storage and Accountability

- The investigator or designee must confirm appropriate temperature conditions have been maintained during transit for all enfortumab vedotin received and any discrepancies are reported and resolved before use of the enfortumab vedotin.
- Only participants enrolled in the study may receive enfortumab vedotin and only authorized study site personnel may administer enfortumab vedotin. Only study drug with appropriate expiry/retest dating may be dispensed.
- All enfortumab vedotin must be stored in a secure, environmentally controlled and monitored (manual or automated) area in accordance with the labeled storage conditions and access must be limited to the investigator and authorized study site personnel.
- The investigator, institution or the head of the medical institution (where applicable) is responsible for accountability, reconciliation and record maintenance (i.e., receipt, reconciliation and final disposition records).
- Further guidance and instruction on final disposition of used and unused study drug is provided in the pharmacy manual.

Refer to the pharmacy manual for detailed information regarding handling, storage and accountability of the enfortumab vedotin.

6.3 Randomization and Blinding

This is an open-label, single-arm study. Participant enrollment and dispensation of enfortumab vedotin will be performed via the interactive response technology (IRT) system. Specific IRT procedures will be described in the respective study manual.

6.4 Investigational Product Compliance

The dose and schedule of enfortumab vedotin administered to each participant will be recorded on the eCRF for each dose. Reasons for dose delay, reduction or omission will be documented.

6.5 Dose Modification

Intrapatient dose reduction to 1 mg/kg (dose level -1), and to 0.75 mg/kg (dose level -2) will be allowed depending on the type and severity of toxicity. Participants requiring a

dose reduction may be re-escalated by 1 dose level (e.g., participants reduced to 0.75 mg/kg may only be re-escalated to 1 mg/kg) provided the toxicity does not require study drug discontinuation and has returned to baseline or \leq Grade 1. If the toxicity recurs, re-escalation will not be permitted. Participants with \geq Grade 2 corneal AEs will not be permitted to dose re-escalate.

Dose modification recommendations for enfortumab vedotin associated toxicity (hematologic and non-hematologic, by National Cancer Institute-common terminology criteria for adverse event [NCI-CTCAE] v4.03 grade) are presented in [Table 7](#) and [Table 8](#).

If toxicities present on Day 1 of any cycle and require the enfortumab vedotin dose to be held, then the start of the cycle may be delayed. If toxicities present on Days 8 or 15 of any cycle and require the dose to be held $>$ 2 days, then the dose(s) must be eliminated, rather than delayed. If a participant only receives enfortumab vedotin on Day 1 and needs to skip Days 8 and 15, the participant could resume the next cycle as early as Day 22 (new Day 1) if the toxicity has resolved by that time.

Treatment break, dose reduction or delay for other enfortumab vedotin associated toxicities is permitted at the discretion of the investigator. Medical Monitor consultation is required after the participant was unable to receive one full cycle of study drug administration. (i.e., 3 consecutive doses) for toxicities or any other reasons. If participant was unable to receive study drug \geq 2 cycles (i.e., \geq 6 consecutive doses not received) for toxicity or for any other reasons, the participant will be discontinued. Dose delays for participants who are responding to treatment may be extended beyond 8 weeks in consultation with Medical Monitor, if the participant's toxicity does not otherwise require permanent discontinuation.

Disease assessment must continue to be performed at the protocol specified frequency and will not be adjusted while participant is not receiving study treatment or any dose delay. It will continue to be timed from Cycle 1 Day 1 during treatment.

The treatment could be continued until any of the study discontinuation criteria is met.

Participants may not receive other investigational drugs and/or vaccines, radiotherapy (except palliative radiotherapy as described in Section [6.8.1](#)), or systemic antineoplastic therapy during dose delays.

Dose modification recommendations for enfortumab vedotin associated toxicity are presented in [Table 7](#) below.

Table 7 Recommended Dose Modifications for Enfortumab Vedotin Associated Hematologic Toxicity*

Grade 1	Grade 2	Grade 3	Grade 4
Continue at same dose level.	Continue at same dose level. For Grade 2 thrombocytopenia withhold dose until toxicity is \leq Grade 1 or has returned to baseline, then	Withhold dose until toxicity is \leq Grade 1 or has returned to baseline, then resume treatment at the same dose level or consider dose reduction by 1 dose level.	Withhold dose until toxicity is \leq Grade 1 or has returned to baseline, then reduce dose by 1 dose level and resume treatment or discontinue at the discretion of the investigator. Transfusions or growth factors may be used as indicated per

Grade 1	Grade 2	Grade 3	Grade 4
	resume treatment at the same dose level.	Transfusions or growth factors may be used as indicated per institutional guidelines.	institutional guidelines. For anemia, treatment discontinuation should be strongly considered.

*Hematologic toxicity refers to anemia, thrombocytopenia, neutropenia and febrile neutropenia.

Table 8 Recommended Dose Modifications for Enfortumab Vedotin Associated Non-hematologic Toxicity

Any Grade			
Grade 1	Grade 2	Grade 3	Grade 4

Continue at same dose level.
 
For Grade 1 rash or skin reactions, the subject may continue at the same dose level. See also [Section 6.5.1] for recommended management of rash.
 
If ocular symptoms and/or changes in vision are identified, the participant should be evaluated with an ophthalmologic exam.*
	
Continue at same dose level, except in the event of Grade 2 neuropathy or corneal AEs.
 
For worsening rash or skin reactions, or skin reactions with concomitant fever, withhold enfortumab vedotin until toxicity is \leq Grade 1 or has returned to baseline, and then resume treatment at the same dose level or
	
Withhold dose until toxicity is \leq Grade 1 or has returned to baseline, then resume treatment at the same dose level or consider dose reduction by 1 dose level.**
 
For Grade 3 rash or skin reactions, withhold enfortumab vedotin until toxicity is \leq Grade 1 or has returned to baseline, and then resume treatment at the same
	
For Grade 4 AEs, discontinue treatment.**
 
For confirmed SJS or TEN, or Grade 4 rash or skin reactions, permanently discontinue treatment.
 
Grade 4 vomiting and/or diarrhea that improves to \leq Grade 2 within 72 hours with supportive management does not require discontinuation.

Table continued on next page

Grade 1	Grade 2	Grade 3	Grade 4
	
consider dose reduction by 1 level. Consider referral of the subject to a dermatologist/specialist for diagnosis and specialized care.
 
For Grade 2 neuropathy or corneal AEs, withhold dose until toxicity is \leq Grade 1 or has returned to baseline, and then resume treatment at the same dose level. For the second occurrence of Grade 2 neuropathy or corneal AE's withhold dose until toxicity is \leq Grade 1, and then reduce the dose by 1 dose level and resume treatment.
 
If ocular symptoms and/or changes in vision are identified, the participant should be evaluated with an ophthalmologic exam.*
	
dose level or consider dose reduction by 1 level. Consider referral of the subject to a dermatologist/specialist for diagnosis and specialized care.
 
Subjects who have confirmed SJS or recurrent \geq Grade 3 rash events should have therapy permanently discontinued.
 
For Grade 3 neuropathy or corneal AEs, discontinue treatment.
 
For Grade 3 hyperglycemia/elevated blood glucose, withhold study treatment. Resume treatment once hyperglycemia/elevated blood glucose has improved to \leq Grade 2 and participant is clinically and metabolically stable.
 
If ocular symptoms and/or changes in vision are identified, the participant should be evaluated with an ophthalmologic exam.*
	
For Grade 4 hyperglycemia/elevated blood glucose, withhold enfortumab vedotin treatment and undertake a full evaluation of the hyperglycemia event. Once the blood glucose levels return to Grade 2 drug dosing may be resumed with close monitoring after consultation with medical monitor.

AEs: adverse events; SJS: Stevens-Johnson Syndrome; TEN: toxic epidermal necrolysis

* Ophthalmologic exam should be performed by an ophthalmologist. If optometrists can perform exams and prescribe medications, an optometrist may be used instead.

** Grade 3/4 electrolyte imbalances/laboratory abnormalities that are not associated with clinical sequelae and/or are corrected with supplementation/appropriate management within 72 hours of their onset do not require discontinuation (e.g., Grade 4 hyperuricemia). Grade 3 or 4 elevations of amylase or lipase, if asymptomatic do not require treatment delay or treatment discontinuation.

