6.5.1 Enfortumab Vedotin-Related Rash

Enfortumab vedotin is a Nectin-4 directed antibody drug conjugate. Nectin-4 is a cell adhesion molecule that is highly expressed in urothelial carcinoma. Low to moderate levels of Nectin-4 are also expressed on normal tissues, including skin keratinocytes, sweat glands and hair follicles; thus, skin reactions are anticipated events. As such, skin reactions are AEs of interest in all clinical studies with enfortumab vedotin.

A cumulative review of post-marketing safety data from 18 Dec 2019 (the approval date of enfortumab vedotin in the US) through 22 Oct 2020 identified reports of severe cutaneous adverse reactions in 15 subjects receiving enfortumab vedotin, some of whom had fatal outcomes. These reactions occurred predominantly during the first cycle of

treatment. AEs reported in these cases included Stevens-Johnson Syndrome (SJS) (5 cases), blister (3 cases), dermatitis bullous (3 cases), symmetrical drug-related intertriginous and flexural exanthema (SDRIFE; 2 cases), and 1 case each of dermatitis exfoliative, exfoliative rash, epidermal necrosis, oropharyngeal blistering, stomatitis and toxic epidermal necrolysis (TEN).

In enfortumab vedotin monotherapy studies of urothelial carcinoma, SAEs of severe cutaneous adverse reactions were reported in 11 of 749 subjects (1.5%) and included dermatitis bullous (0.4%), drug eruption (0.4%), blister (0.1%), conjunctivitis (0.1%), SJS (0.1%), stomatitis (0.1%) and toxic skin eruption (0.1%).

Subjects should be informed that rash and severe skin reactions have occurred after administration of EV, and to contact the Investigator immediately if they have signs and symptoms of skin reactions, oral mucosal and ocular abnormalities including mucositis or conjunctivitis. Starting in the first cycle and throughout treatment, closely monitor subjects for skin reactions. For mild to moderate skin reactions, consider appropriate treatment, such as topical corticosteroids and antihistamines as clinically indicated. For recommendations regarding dose modifications for skin reactions due to EV, refer to [\[Table 8\]](#).

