6.5.2 Management of Hyperglycemia

Investigators should monitor blood glucose levels and are advised to perform additional assessments if any symptoms of hyperglycemia are observed, including a thorough evaluation for infection. In addition, if steroids are used to treat any other condition, blood glucose levels may require additional monitoring. If elevated blood glucose levels are observed, participants should be treated according to local standard of care and referral to endocrinology may be considered.

Participants, especially those with a history of or ongoing diabetes mellitus or hyperglycemia, should be advised to immediately notify their physicians if their glucose level becomes difficult to control or if they experience symptoms suggestive of hyperglycemia such as frequent urination, increased thirst, blurred vision, fatigue, and headache. Participants who enter the study with an elevated HbA1c ($\geq 6.5\%$) at baseline should be referred to an appropriate provider during Cycle 1 for glucose management. Blood glucose should be checked prior to each dosing and dose should be withheld for blood glucose > 250 mg/dL (13.9 mmol/L) (Grade 3 or higher). Dosing may continue once the participant's blood glucose has improved to \leq Grade 2 and participant is clinically and metabolically stable. Blood glucose > 500 mg/dL (27.8 mmol/L) (Grade 4) considered related to enfortumab vedotin requires treatment discontinuation. If a participant experiences new onset of diabetes mellitus, evaluate participants with a metabolic panel, urine ketones, HbA1c, and C-peptide to assess for new onset diabetes.

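### Table 8 allows redosing after drug-related Grade 4 hyperglycaemia where Section 6.5.2 requires treatment to stop; the missed-dose limit also differs between sections

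*Protocol*

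**What the plan says.** **Hyperglycaemia.** The table is headed "Table 8 Recommended Dose Modifications for Enfortumab Vedotin Associated Non-hematologic Toxicity". Its Grade 4 column opens with a general instruction to stop treatment for Grade 4 events, then gives hyperglycaemia its own text. The site is told to "withhold enfortumab vedotin treatment and undertake a full evaluation of the hyperglycemia event", and then: "Once the blood glucose levels return to Grade 2 drug dosing may be resumed with close monitoring after consultation with medical monitor".

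Section 6.5.2 covers the same event. It withholds dosing for glucose above 250 mg/dL (Grade 3 or higher) and lets dosing continue once glucose is at or below "Grade 2 and participant is clinically and metabolically stable". It then adds: "Blood glucose > 500 mg/dL (27.8 mmol/L) (Grade 4) considered related to enfortumab vedotin requires treatment discontinuation". Section 8.1 defines discontinuation from treatment as permanent.

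**Missed doses.** Section 6.5 puts a greater-than-or-equal sign in front of "6 consecutive doses not received) for toxicity or for any other reasons, the participant will be discontinued". Sections 1.1, 4.1 and 8.1 use a strict greater-than sign with the same number. All four sections let responders exceed 8 weeks after consultation with the medical monitor.

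**SAP.** Section 4.2.2 counts, as category PD2, participants who met a withdrawal criterion and were not withdrawn.

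**The concern.** A participant with drug-related Grade 4 glucose that recovers to Grade 2 may be redosed under one text and must stop for good under the other. Hyperglycaemia is a named risk of this drug (Sections 2.3.1 and 2.3.3) and an adverse event of special interest in SAP Section 4.5, so the rule is likely to be consulted.

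Table 8 also leaves the requirement for clinical and metabolic stability out of its Grade 4 text, although its Grade 3 column includes it. Read alone, the table sets one condition fewer for the worse event.

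The missed-dose mismatch is smaller. A non-responder who has missed exactly 6 consecutive doses must stop under Section 6.5 but not under the other three sections.

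What is at stake is participant safety and consistent conduct, and after that the consistency of a descriptive deviation count.

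**Working it through.** **1. Hyperglycaemia: the two texts compared**

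| Item | Table 8, Grade 4 | Section 6.5.2 |
|---|---|---|
| Scope | Drug-associated toxicity, by title | Glucose above 500 mg/dL considered drug-related |
| First step | Withhold and evaluate | Withhold (applies to Grade 3 or higher) |
| After recovery to Grade 2 | May resume after consultation | Related Grade 4: must discontinue |
| Depends on relatedness | No | Yes |
| Stability required before resuming | Not stated for Grade 4 | Yes |
| Refers to the other text for hyperglycaemia | No | No |

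Drug-related events are the subject of Table 8, so a site cannot infer that its Grade 4 text is meant only for unrelated ones. The protocol does link the two places where it wants them read together. For rash, the table says "See also [Section 6.5.1] for recommended management of rash", and Section 6.5.1 replies "For recommendations regarding dose modifications for skin reactions due to EV, refer to" Table 8. Hyperglycaemia has no such link in either direction.

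**2. How many participants**

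The documents give no rate for drug-related Grade 4 hyperglycaemia. Section 2.2.4 gives 7% for Grade 3 or higher hyperglycaemia of any cause in EV-201 Cohort 1. If that rate applied here, 0.07 × 40 = 2.8 participants would be expected. Drug-related Grade 4 events are a subset of these, and the conflict also needs recovery to Grade 2 and a decision to redose.

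Effect on PD2 with 40 enrolled: 1/40 = 2.5 percentage points for a participant who is redosed, and 0 for one who is stopped.

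**3. Missed doses: planned calendar**

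Two cycles × 3 doses = 6 doses, so the limits disagree only at exactly 6. With dosing on Days 1, 8 and 15 of 28-day cycles, and counting the first dose as day 0, planned doses fall on days 0, 7, 14, 28, 35, 42, 56, 63, 70, 84 and 91. Visit windows and delayed cycle starts are ignored. The gap is the next planned dose day minus the day of the last dose given.

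| Last dose given | 5 missed | 6 missed | 7 missed |
|---|---|---|---|
| Day 1 (day 0) | 56 − 0 = 56 | 63 − 0 = 63 | 70 − 0 = 70 |
| Day 8 (day 7) | 63 − 7 = 56 | 70 − 7 = 63 | 84 − 7 = 77 |
| Day 15 (day 14) | 70 − 14 = 56 | 84 − 14 = 70 | 91 − 14 = 77 |

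Stopping at 6 or more allows redosing after at most 5 missed doses, a gap of 56 days. Stopping at more than 6 allows it after 6, a gap of 63 or 70 days. The difference is 63 − 56 = 7 to 70 − 56 = 14 days.

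The 8-week sentence for responders does not decide between the limits. Counted from the first missed planned dose, 6 missed doses is 63 − 7, 70 − 14 or 84 − 28, each 56 days or exactly 8 weeks. Counted from the last dose given, it is 63 or 70 days.

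**The case against.** The strongest reply is that the two hyperglycaemia texts can be obeyed together. Table 8 only permits resumption, and only after a full evaluation and consultation. Section 6.5.2 is mandatory for related events. Evaluate first, stop if related, and otherwise resume: that satisfies both, and stopping always complies. The table is headed as recommended while Section 6.5.2 uses the language of requirement, and the general Grade 4 line in the table also says to stop.

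This is probably what was intended, and it limits the practical risk. It does not remove the conflict. The reading needs a relatedness condition that the table lacks, and no text gives an order of precedence. A specific resume rule placed after a general stop rule reads as an exception to it. The medical monitor would be working from the same two texts.

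The table's footnote excusing laboratory abnormalities that lack clinical sequelae or are corrected within 72 hours does not settle the matter either. In the Grade 4 column it is attached to the general line and not to the hyperglycaemia text.

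Three smaller objections have force:

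- The missing stability condition is supplied by Section 6.5.2 for anyone who reads it, so it is a symptom of the missing link and not a separate gap.
- The missed-dose difference is one dose at a boundary, and consultation is already required after 3 missed doses. If PD2 is taken from the mandatory list in Section 8.1, only one limit (more than 6) applies to that count.
- The calendar figures assume the planned schedule. Section 6.5 lets a participant who skips Days 8 and 15 restart as early as Day 22. On that schedule (last dose on day 0, then planned doses on days 7, 14, 21, 28, 35, 49 and 56) the gaps are 49 days after 5 missed doses and 56 after 6. The limits still differ by 7 days.

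**Conclusion.** The concern holds, as a minor one. Table 8 as written permits redosing that Section 6.5.2 forbids, in a table confined to drug-associated events and with nothing to say which text prevails. The missed-dose limits disagree at exactly 6 doses for participants outside the responder exception; this is a boundary slip in wording.

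Few participants can be affected, and the number cannot be estimated from the documents. The PD2 figure assumes 40 enrolled and that a Section 6.5.2 stop is treated as a withdrawal criterion. The 7 to 14 days assume the planned calendar. Membership of the full analysis set depends only on enrolment and receipt of drug, so neither that set, nor the power, nor the success rule for confirmed response changes.

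**What to change.** 1. Replace the resumption sentence in the Table 8 Grade 4 hyperglycaemia text with: *If considered related to enfortumab vedotin, discontinue treatment (Section 6.5.2). If not considered related, dosing may restart with close monitoring once glucose is Grade 2 or lower and the participant is stable both clinically and metabolically, after consultation with the medical monitor.* Add a pointer to Table 8 in Section 6.5.2, as Section 6.5.1 already has.
2. Use one missed-dose limit, in identical words, in Sections 1.1, 4.1, 6.5 and 8.1. The clinical team should choose it on safety grounds, and the responder exception should stay.
3. Optionally, have SAP Section 4.2.2 tie PD2 to Protocol Sections 8.1 and 6.5.2.

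The cost is a wording change in an amendment or clarification letter, with no added visits, procedures or participants.
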